Completed by Independent Evaluators															
University of Washington Risk Assessment Protocol (UWRAP)			X			X			X			X			X
Clinical Global Impression – Severity (CGI-S)		X			X			X			X				X

Table 1. Schedule of Activities for the CAMPUS Trial

	-1	0	Stage 1						Stage 2						26	
			1	2	3	4	5	6	7	8	9	10	11	12	14	
Clinical Global Impression – Improvement (CGI-I)					X			X			X				X	X
Scale for Suicidal Ideation (SSI)		X		X			X			X		X			X	X
Self-Injurious Thoughts and Behaviors Interview (SITBI)	X						X			X			X		X	X
Global Assessment Scale (GAS)		X		X			X			X		X			X	X
Treatment History Interview (THI)	X														X	X
Completed by Research Staff																
Informed Consent		X														
Inclusion/Exclusion Checklist		X														
CAMS Rating Scale-3 ¹																
DBT Adherence Rating Scale ¹																
Completed by Counselor Participants																
Reveal Randomization			X						X							
Demographic Information Form (DIF) ²		X														
Treatment Compliance Item*			X	X	X	X	X	X	X	X	X	X	X	X	X	
AE/SAE Summary Form			X	X	X	X	X	X	X	X	X	X	X	X	X	
Clinical Global Impression – Severity (CGI-S) ³			X					X								X
Clinical Global Impression – Improvement (CGI-I)				X	X	X	X	X	X	X	X	X	X	X	X	
Treatment Assignment Reaction Form		X							X							
Counselor Treatment Expectations Questionnaire (CTEQ)		X							X							
Client Satisfaction Questionnaire-Counselor (CSQ-C) and Counselor Satisfaction Rating ³								X								X
Reasons for Termination Checklist ³								X								X
TAU Questionnaire ³									X							
Counselor Telehealth Questionnaires (CTSQ) ³																X
Zero Suicide Workforce Survey- Abbreviated (ZSWS) ⁴	X															X
Focused Interview ⁵																X

Table 1. Schedule of Activities for the CAMPUS Trial

	Stage 1						Stage 2									
	-1	0	1	2	3	4	5	6	7	8	9	10	11	12	13	14
Notes (1): 1. Research staff will complete this measure on a random sample of therapy sessions. 2. Counselor participants will complete this measure once when they enter the study. 3. Counselor participants will complete this measure following students' last treatment session which may be earlier than Week 14. 4. Counselor participants will complete this measure at the start of their participation in the study and then every six months. 5. Counselor participants will complete this interview at the end of their participation in the study.																

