8 STUDY ASSESSMENTS AND PROCEDURES

8.1 ENDPOINT AND OTHER NON-SAFETY ASSESSMENTS

We have divided measures into demographics, primary and secondary dependent variables (DVs), mediators, moderators, and implementation/process variables. Measures were selected if they: 1) fit the study aims, 2) have adequate psychometrics, 3) are listed as Common Data Elements in NIH or have been used in previous SR studies, 4) have shown sensitivity to change, 5) have been used with college students, 6) map onto the RDoC categories (Negative Valence Systems, Positive Valence Systems, Cognitive Systems, Social Processes, and Arousal and Regulatory Systems),⁷⁹ 7) are directly relevant to the application of CAMS or DBT, and 8) allow for reduced burden to student participants—the latter in response to reviewers' concerns.

Demographic Variables.

With student participants' consent, age, marital status, family income, residence, GPA, race, year in school, major, ethnicity, sexual orientation, cultural identity, and gender identity will be obtained via EMR/the registrar or by completing the Demographic Information Form at baseline.

SMART Primary Tailoring Variable: Sufficient vs. Insufficient Response to Stage 1 Treatments. Unique to SMARTs are tailoring variables or variables upon which subsequent randomizations are based.⁵⁹ For this trial, sufficient treatment response will be the primary tailoring variable and assessed by the Clinical Global Impressions (CGI),¹⁰³ adapted to SR. As noted in Preliminary

Studies, the CGI, adapted to SR, showed high inter-rater reliability and construct validity; this fits with other studies demonstrating that non-blinded trained counselors typically can offer CGI ratings commensurate to blinded IEs.¹¹¹

In SMARTs, a tailoring variable is a tool for clinical decision-making, in this case deciding on response to treatment, and therefore it will be based on clinical assessments by providers (and not the IE).⁵⁹ Beginning at session 4 and following each subsequent session, the counselor will complete the 7-point Likert-style CGI developed in the CAMPUS feasibility study to rate overall improvement in SR since baseline from (1) “*Very much improved*” to (7) “*Very much worse*.” Sufficient response will be defined as an Improvement score of ≤ 2 (“*Much improved*” or “*Very much improved*”).

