Aim 2 analyses will contrast ATSSs beginning with CAMS vs. interventions beginning with TAU (i.e., to evaluate the main effect of initial treatment) on change (decrease) in suicide-related risk behaviors (SI, NSSI, and suicide attempts—the primary outcomes) from baseline to the end of Stage 2 (the primary contrast). This is a comparison of cells A+B+C vs. D+E+F (see Figure 2 and Table 8). Note that the primary continuous longitudinal outcome is assessed at baseline, mid-Stage 1 (3 weeks), post Stage 1 (6 weeks), mid-Stage 2 (10 weeks), post-Stage 2 (14 weeks) (end of acute treatment) and then again at 3-month follow-up (26 weeks), for a total of 6 measurement occasions. Linear mixed models¹⁶³ (LMM, also known as random effects or growth curve models), fit with SAS PROC MIXED will be used to analyze the longitudinal data. LMMs use all available measurements, allowing student participants to have an unequal number of observations and producing unbiased parameter estimates as long as unobserved values are missing at random. The analysis will fit a LMM with fixed effects for the intercept, time, group, and a group-by-time interaction term, where group is an indicator of phase-one treatment (CAMS vs. TAU as referent). The LMM will also include random effects for the intercept and time and an unstructured within-person correlation structure for the residual errors and will adjust for the following measures collected at baseline (pre-randomization): site, age, race, and clinical severity. Model diagnostics will be used to determine suitability of more parsimonious (e.g., autoregressive) correlation structures, and nonlinear (e.g., quadratic) effects for time. We do not expect the intervention effects to be attenuated due to counselor participants who are cross classified between the interventions. Nonetheless, we will assess the potential attenuation by assessing the counselor x intervention interaction. If significant, we will examine if the attenuation effect is limited to a select few counselors and eliminate as needed to remove potential counselor contamination of intervention effects. Counselor will be treated as a random effect which models potential correlation between student participants within a common counselor. If there is not sufficient variance, indicated by the reliability estimate of the random effect falling below 0.02 (a slighter lower threshold compared to

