Raudenbush and Bryk¹⁶⁴ (p.125), we will treat counselor as a fixed effect. The primary contrast is between groups' difference in change from baseline to month 6 (end of acute treatment through Stage 1 and Stage 2 active treatment). The follow-up contrast at week 26 (12 weeks post-acute treatment) will also be examined in this and in all subsequent analyses. LMMs like the above for the primary outcome will be run for the secondary longitudinal outcomes: CAMS vs. TAU on CCAPS subscales (Depression, Anxiety, Academic Distress, Overall Distress), CGI-I and CGI-S (measured by IE), and cumulative GPA.

AIM 3 analyses will examine the relative effectiveness of switching to a more comprehensive suicide-focused treatment approach (e.g., CC-DBT) among those who do not respond sufficiently to Stage 1 treatments vs. a less intensive suicide-focused approach (e.g., CAMS). This analysis is a comparison of cells C+F (switch to CC-DBT) vs. B+E (switch or continue with CAMS) in Table 8. Both primary and secondary longitudinal outcomes outlined above will be examined using an LMM like that described above, but (a) including only the subset of responders to Phase 1 treatment, (b) defining group as switching to CC-DBT (cells C+F) vs. continuing or switching to CAMS (cells B+E), and (c) using monthly longitudinal outcomes from week 4 to week 24 (7 measurement occasions).

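### For IE-rated CGI-I, the Aim 2 change-from-baseline contrast has no baseline to start from; the contrast should be the group difference in level at week 14

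*Combined protocol and SAP*

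**What the plan says.** The Aim 2 model in section 9.3.2 has "fixed effects for the intercept, time, group, and a group-by-time interaction term", with group meaning the Stage 1 assignment (CAMS or TAU). One contrast is named for it: "The primary contrast is between groups' difference in change from baseline to month 6". The same sentence glosses that time point as the end of acute treatment. Month 6 does not match the 14-week end of Stage 2 given elsewhere, but this does not affect the present point.

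The plan then states: "LMMs like the above for the primary outcome will be run for the secondary longitudinal outcomes". The list includes "CGI-I and CGI-S (measured by IE), and cumulative GPA". CGI-I receives no model or contrast of its own. Section 9.3.3 refers back to the same analyses for Aims 1 to 3, and the Aim 3 paragraph reuses a similar model for the secondary outcomes.

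Section 8.1 describes the counselor's CGI-I as a seven-point scale used to "rate overall improvement in SR since baseline". In Table 1 (section 1.3), the independent evaluators' row for "Clinical Global Impression – Improvement (CGI-I)" carries five marks, none in the baseline area. The row for "Clinical Global Impression – Severity (CGI-S)" begins with a baseline mark. Column alignment is imperfect in the text I worked from, but the student-completed rows show the same pattern. Section 4.2 sets evaluator assessments at baseline and weeks 3, 6, 10, 14 and 26, so five CGI-I ratings fit the five post-baseline visits.

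**The concern.** Change from baseline suits an outcome that is measured at baseline and then again later. CGI-I is different: each rating is already a judgment of change since baseline, so the treatment effect is the difference between arms in the rating itself.

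Under the named contrast, two things can happen. A change from week 0 can be read off the fitted line, which extrapolates to a time when nothing was rated. Or the group-by-time term can be tested, which asks whether the gap in improvement widens from visit to visit. Neither asks whether one arm improved more.

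The design makes this more than a formality. Randomized Stage 1 treatment lasts 4 to 6 weeks. After that, responders in both arms enter maintenance and non-responders in both arms are re-randomized to the same two options. An advantage of CAMS over TAU could appear early and then level off, and a slope contrast picks up that shape poorly.

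**Working it through.** **Inputs from the documents.** 240 per Stage 1 arm, two-sided alpha 2.5%, d = 0.30 and 85% power (section 9.2, Aim 2); evaluator visits at weeks 3, 6, 10, 14 and 26 (section 4.2).

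**Assumptions.** d = 0.30 is stated for the primary outcomes and is borrowed here. The within-person correlation ρ runs from 0.3 to 0.6; section 9.2 mentions 0.3, 0.40 and 0.60, none of them for CGI-I. I take SD 1, equal correlation between visits and no missing data. The critical value is z = 2.241.

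**Step 1: the plan's own figure.** For a single comparison of means, SE = √(2/240) = 0.0913 and 0.30/0.0913 = 3.286. Power = Φ(3.286 − 2.241) = 85.2%. The stated 85% reproduces, and the same figure applies to a week-14 difference in CGI-I level using week 14 alone.

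**Step 2: constant difference of 0.30 SD from week 3 onward.** The between-group difference in slope has expected value exactly 0, so the group-by-time test rejects at its alpha, 2.5%. This holds for every ρ tried (0.3, 0.4, 0.6), with or without week 26. A simulation of 5,000 trials (ρ = 0.4, weeks 3-14) gave 2.2% for the slope and 85.7% for the week-14 level.

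**Step 3: difference growing linearly from 0 to 0.30 SD at week 14, visits at weeks 3, 6, 10, 14.** The mean visit time is 8.25 weeks, and the sum of squared deviations is 27.5625 + 5.0625 + 3.0625 + 33.0625 = 68.75.

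- Slope contrast over 14 weeks: SE = 14 × √[2(1 − ρ)/(240 × 68.75)].
- Level at week 14 from the same line: SE = √{2(1 + 3ρ)/(4 × 240) + (14 − 8.25)² × 2(1 − ρ)/(240 × 68.75)}.

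The true value of both is 0.30.

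| ρ | SE, slope | Power, slope | SE, level | Power, level |
|---|---|---|---|---|
| 0.3 | 0.129 | 53% | 0.082 | 92% |
| 0.4 | 0.119 | 61% | 0.084 | 91% |
| 0.6 | 0.097 | 80% | 0.086 | 89% |

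**Step 4: an intermediate shape.** With 0.15 SD at week 3 and 0.30 SD from week 6 onward, the slope contrast has about 10-28% power over the same range of ρ, with or without week 26. Week 14 alone still gives 85%.

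**Step 5: adding week 26 to a straight line.** With a constant difference, the week-14 level from the line has 96-99.6% power. If the difference grows to week 14 and then stays flat, the straight line fits badly. It puts the week-14 level at 0.224 instead of 0.30, with power 92%, 87% and 76% at ρ = 0.3, 0.4 and 0.6, against 55%, 62% and 81% for the slope. At ρ = 0.6 the advantage of the level contrast is lost. That comes from the linear time term, and the observed week-14 means still give 85%.

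**The case against.** The strongest reply is that the plan does not say the contrast is copied. It says the models will be like the primary one, it does not restate the contrast for secondary outcomes, and a change from an unmeasured baseline cannot be computed literally. This stands in part: a sensible analyst might compare levels. But no other contrast is written, so that choice would be made after the data are in.

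Second, the fitted model contains a group term, and a constant difference sits there. With week 26 included and ρ = 0.5, that term has about 92% power with time coded from week 0 and about 98% with time centered at week 14. This also stands: the information is in the fit. It is not the named contrast, however, and with time coded from baseline the group term is the gap at week 0, where no rating exists.

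Third, Aim 1 compares the four strategies by weighted means and extends similar analyses to the secondary outcomes. That comparison is sound for CGI-I, but it does not answer the Aim 2 question.

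Fourth, the wording about improvement since baseline describes the counselor's rating, whereas Aim 2 analyzes the evaluator's. The documents do not define the evaluator version separately. Section 8.1 treats the CGI as one measure completed by several raters, and Table 1 supports the same reading.

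A reader might infer that the trial would miss a real CGI-I effect altogether. The documents do not support that. Total loss needs a difference fully present by week 3 and unchanged afterward, and nothing in the plan predicts that course. Section 9.3.2 also allows nonlinear time effects.

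**Conclusion.** The point holds in a limited form. As written, Aim 2 assigns IE-rated CGI-I a contrast that does not fit a measure of improvement with no baseline value. Under the borrowed d = 0.30 and ρ from 0.3 to 0.6, the cost ranges from total for a constant difference (2.5% against 85%) to partial for linear growth to week 14 (about 53-80% against 89-92%, weeks 3-14). The true shape of the difference is unknown, so no single figure in that range can be called the expected loss.

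The fault is confined to the named contrast for one secondary outcome. CGI-S and CCAPS have baselines and are unaffected, as is the primary outcome. Aim 3 inherits the gap because it reuses the model without restating a contrast. If its change were counted from Stage 2 entry, an earlier CGI-I rating could serve as the starting value, so the figures above apply to Aim 2 only. This is a desirable clarification and does not threaten the trial's main conclusions.

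**What to change.** Add a sentence to section 9.3.2. For CGI-I, the contrast is the model-based between-group difference in level at week 14, with week 26 as the follow-up contrast, estimated from post-baseline visits only. Name baseline CGI-S as the clinical-severity covariate that the model already plans to include. State the corresponding level contrast for Aim 3. Keep the change-from-baseline contrast for outcomes that have a baseline, such as CGI-S and CCAPS.

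Categorical visits are optional. They avoid the straight-line distortion shown in step 5 when week 26 is in the model; a linear model with the week-14 difference stated would also meet the main point.

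The cost is SAP wording only: no new data, visits or participants. It should be settled before outcome data are examined by arm.

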9.3 CAMPUS TRIAL STATISTICAL ANALYSES

9.3.1 GENERAL APPROACH

Overview and Intent-to-Treat. The proposed trial design of adaptive treatment strategies (ATSSs) is like a factorial design;^{156,157,158,159} different analytic subgroups (see Table 8) are combined to answer different questions. Aim 1 is the trial's primary aim; Aims 2-5 are secondary aims and Aim 6 as an implementation aim. All student participants, once randomized, will be included in the intent-to-treat sample, and every effort will be made to collect all primary and secondary outcomes even if a student participant does not engage in randomly assigned treatments. The primary outcome of interest is suicidal risk, which includes suicidal ideation as well as suicide-related behaviors, such as non-suicidal self-injury (NSSI) and suicide attempts (SAs); however suicidal ideation is the primary DV due to relatively low rates of suicidal behaviors post-baseline with college students. Suicides will be tallied as well. All analyses allow for the inclusion of covariates listed as demographics and covariates in Section 8.1. Covariates will enter the model based in clinical importance (gender, age, current alcohol use, current substance use, etc.) and retained on a case-by-case basis based on statistical significance.

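### The Aim 3 model text names the wrong analysis set and a visit grid the trial does not have, and it inherits a wrong label for the end of treatment

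*Combined protocol and SAP*

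**What the plan says.** Section 9.3.1 ranks the aims: "Aims 2-5 are secondary aims and Aim 6 as an implementation aim". Aim 3 is therefore secondary. It is the test of Hypothesis 3 in Table 2, that CC-DBT does better than CAMS at Stage 2.

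The Aim 3 paragraph in Section 9.3.2 poses its question "among those who do not respond sufficiently to Stage 1 treatments" and compares cells C+F with cells B+E of Table 8. It takes over the Aim 2 mixed model with three stated changes:

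- Items (a) and (b), population and grouping: "including only the subset of responders to Phase 1 treatment, (b) defining group as switching to CC-DBT (cells C+F") against cells B+E.
- Item (c), visits: "using monthly longitudinal outcomes from week 4 to week 24 (7 measurement occasions").

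The Aim 2 text that it builds on gives the main comparison as change "from baseline to the end of Stage 2 (the primary contrast"). It lists the assessments at baseline and weeks 3, 6 and 10, then "post-Stage 2 (14 weeks) (end of acute treatment) and then again at 3-month follow-up (26 weeks), for a total of 6 measurement occasions". Further on, the same Aim 2 text describes the primary contrast as the "difference in change from baseline to month 6 (end of acute treatment through Stage 1 and Stage 2 active treatment"). It then adds: "The follow-up contrast at week 26 (12 weeks post-acute treatment) will also be examined in this and in all subsequent analyses".

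**The concern.** Items (a) and (c) are operative: they tell the programmer which students and which records enter the model. Item (a) contradicts the question stated in its own paragraph. Item (c) describes a schedule that does not match the one in Section 4.2 or in the Aim 2 text. The contrast label taken over from Aim 2 places the end of acute treatment at month 6, close to the week 26 follow-up, although the same section places it at week 14.

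The model cannot be run on the SSI or SITBI as specified, so someone has to rewrite it. If that happens after outcome data are available, the visit set and the starting point for change become choices made with the results in view. The effect reaches beyond Aim 3. Section 9.3.3 sends the secondary endpoints to the same analyses and builds the Aim 5 moderator models by adding terms to the outcome models already described.

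**Working it through.** **Item (a), analysis set.** Setting the places side by side:

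| Place | Population |
|---|---|
| Table 8, cells A and D | Responders |
| Table 8, cells B, C, E and F | Insufficient responders |
| Table 2, Hypothesis 3 | Insufficient responders |
| Section 9.2, power for Aim 3 | Non-responders |
| Section 9.3.7, Aim 8, Stage 2 | Non-responders |
| Section 9.3.2, Aim 3, item (a) | Responders |

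Restricting to responders leaves 0 students in B, C, E and F. Restricting to insufficient responders gives the number used in Section 9.2: 480 × 0.50 = 240, less 25% attrition = 180, or about 90 against 90.

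**Item (c), number of occasions.** The plan's figure is 7.

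- Four-weekly from week 4 to week 24: 4, 8, 12, 16, 20, 24, which is 6 points.
- Calendar months of 52/12 weeks from week 4: 4.0, 8.3, 12.7, 17.0, 21.3, which is 5 points.
- Seven points need a start at week 0 (0 to 24) or an end at week 28 (4 to 28). Neither is what the text says.

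The stated 7 is not reproduced from the stated span.

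**Item (c), match with the schedule.** Section 4.2 and the Aim 2 text agree on evaluator visits at weeks 0, 3, 6, 10, 14 and 26.

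- Four-weekly grid points that are scheduled visits: 0 of 6.
- With the ±1 week window in the Schedule of Activities notes, only week 4 touches a visit (the late edge of week 3).
- Visits outside weeks 4 to 24: 0, 3 and 26, which is 3 of 6. Week 0 is where the inherited change starts, and week 26 is the follow-up contrast required in all subsequent analyses.
- Visits inside the span but off the grid: 6, 10 and 14. Week 14 is the end of Stage 2.

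**Inherited label.** The end of acute treatment is week 14 in the Aim 2 list of visits and month 6 in the Aim 2 contrast. Week 26 is defined as 12 weeks after acute treatment, and 26 − 12 = 14. The label is therefore wrong, and week 14 stands.

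**Why the replacement has to be stated.** The Aim 2 model has a linear time term and a group-by-time interaction; curvature is added only if diagnostics suggest it. Illustration, on assumptions of mine: the gap between the arms is 0 up to week 6, rises in a straight line to D at week 14, and stays at D to week 26. An ordinary least-squares line is fitted to the gap, with slope = Sxy/Sxx.

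- Weeks 0, 3, 6, 10, 14, 26, with gaps 0, 0, 0, 0.5D, D, D: Sxy = 20.42D, Sxx = 436.83, slope = 0.0467D per week. Implied change from week 0 to week 14: 14 × 0.0467D = 0.65D.
- Weeks 6, 10, 14, 26, with gaps 0, 0.5D, D, D: Sxy = 10D, Sxx = 224, slope = 0.0446D per week. Implied change from week 6 to week 14: 8 × 0.0446D = 0.36D.

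The true change is D in both cases. The fitted answer depends on the visits and the start. The full mixed model would weight the visits differently, so these figures show that the size can move, not by how much it will move in this trial.

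**The case against.** The best defence is that this is leftover text and the intent is plain. For item (a) and the month 6 label that is right. The same paragraph, Table 8 and the Aim 2 visit list settle both, and an empty analysis set would force correction before any result was reported. A reader might infer that the sponsor would analyse the wrong students; the documents do not support that.

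For item (c) the defence is weaker. One could read weeks 4 to 24 as a window and not as a grid. Weeks 6, 10 and 14 then fall inside it, but that is three visits, neither monthly nor seven, and week 26 is still lost. The SSI row of Table 1 carries seven marks in the text available to me and might be the source of the 7. Its columns are too broken to rely on, and Sections 4.2 and 9.3.2 both list six visits. The CCAPS, a secondary outcome taken at every session, could supply some points between visits; the evaluator interviews could not.

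A reader might also infer that Aim 3 has no starting point for change, or that it conflicts with Aim 8, which measures change from Stage 2 randomisation. Neither goes that far. The start is not among the three stated departures from the Aim 2 model, so study baseline carries over by default; only the faulty grid cuts week 0 out. Aim 8 is exploratory, and having a second version of lower rank is not an error.

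Finally, one might argue that, because students are re-randomised, the starting point affects only precision. That holds for simple change scores or separately estimated visit means. It does not hold in general for the linear-time model that is planned.

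**Conclusion.** The point stands as a specification error that should be fixed, in a secondary aim. Two operative items are wrong as written: the analysis set (0 eligible students if read literally, against about 180 planned) and the visit grid (6 points where 7 are stated, none on the evaluator schedule, with weeks 0 and 26 outside the span). One inherited label is wrong: month 6 should be week 14.

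The conclusion on the grid rests on the visit weeks in Section 4.2 and the Aim 2 text, which agree. No bias in a particular direction is shown. What is shown is that the text cannot be followed for the SSI or SITBI, and that the analyst's replacement could change the size of the estimated effect as well as its precision. The 0.65D and 0.36D figures are illustrative and depend on the assumed course of the gap.

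**What to change.** Change the wording of Section 9.3.2 as follows.

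- Item (a): replace the reference to responders with *insufficient responders re-randomised at Stage 2, analysed as re-randomised*.
- Item (b): no change.
- Item (c): for evaluator-rated outcomes, replace the monthly grid and its count with the visits in the Aim 2 text: weeks 0, 3, 6, 10, 14 and 26, 6 occasions. If CCAPS records between visits are to be used, say so separately.
- Aim 2 contrast label: replace month 6 with week 14.
- Keep the end of Stage 2 as the primary contrast and week 26 as the follow-up, as already planned.
- Add one sentence that confirms study baseline as the start of change for Aim 3, or names another start, before data are seen. If a Stage 2 start is named, define which visit serves as its baseline. Section 4.4 allows re-randomisation soon after session 4, so for some students the last visit before it may be week 3.

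The cost is an edit to the analysis text. It needs no new data, visits or participants.
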